**5.2.1.3 Endocrinopathy:**

Rule out non-inflammatory causes. If non-inflammatory cause, treat accordingly and continue protocol therapy. Consider visual field testing, endocrinology consultation and imaging.

Endocrinopathy	Management	Follow-up
Asymptomatic thyroid-stimulating hormone (TSH) elevation	
 
• Continue nivolumab
 
• If TSH <0.5 x LLN or TSH >2x ULN, or consistently out of range in subsequent measurements, include free T4 in subsequent measurements as clinically indicated
 
• Consider endocrinology consult
 
	
Symptomatic Hypothyroidism	
 
• Initiate thyroid replacement
 
	
Symptomatic Hyperthyroidism	
 
• Delay nivolumab
 
• Consider endocrinology consult
 
	
 
• Resume nivolumab and IL-2 when symptoms of hyperthyroidism are
 

Endocrinopathy	Management	Follow-up
	
 
Initiate anti-thyroid drug
 
	controlled and thyroid function is improving
Hypophysitis	
 
Administer corticosteroids and hormone replacement as clinically indicated
 
Delay nivolumab for grade 2 or 3 hypophysitis
 
Permanently discontinue nivolumab and IL-2 for grade 4 hypophysitis
 
	
Symptomatic Adrenal Insufficiency	
 
Delay nivolumab
 
Administer methylprednisolone 1-2 mg/kg/day IV followed by oral prednisone 1-2mg/kg per day or equivalent once symptoms improve
 
	
 
If improves to <math>\leq</math> grade 1, taper steroids over at least one month
 
Resume nivolumab and IL-2 if the vent improves to grade 0 or 1 within 12 weeks and corticosteroids have been reduced to the equivalent of <math>\leq</math>10 mg oral prednisone per day and the patient is on stable replacement therapy if required
 

**5.2.1.4 Hepatic:**

Rule out non-inflammatory causes. If non-inflammatory cause, treat accordingly and continue protocol therapy. Consider imaging for obstruction.

Grade of Liver Test Elevation (NCI CTCAE v4)	Management	Follow-up
Grade 1 AST or ALT >ULN to 3x ULN and/or total bilirubin >ULN to 1.5x ULN	
 
Continue nivolumab
 
	
 
Continue liver function test monitoring per protocol
 
If worsening, treat as grade 2,3, or 4
 

Grade 2 AST or ALT >ULN to 3-5x ULN and/or total bilirubin >ULN to 1.5-3x ULN	
 
Delay nivolumab
 
Administer corticosteroids at a dose of 1-2mg/kg/day prednisone
 
	
 
Resume nivolumab and IL-2 if returns to baseline
 
If persists >5-7 days or worsens, treat as grade 3 or 4
 

Grade 3 or 4 AST or ALT >5x ULN and/or total bilirubin >3x ULN
	
 
• Discontinue nivolumab
 
• Increase frequency of monitoring to every 1-2 days
 
• 1-2mg/kg/day methylprednisolone IV or IV equivalent for grade 3 and 2 mg/kg/day methylprednisolone IV for grade 4
 
• Add prophylactic antibiotics for opportunistic infections like PCP
 
• Consult gastroenterologist
 
	
 
• If improves to grade 2, taper steroids over at least one month
 
• If does not improve within 3-5 days or worsens after improvement:             
 
○ Add mycophenolate mofetil 1g twice daily
 
○ If no response within an additional 3-5 days, consider other immunosuppressive agents per local guidelines
 
 
 

---	--	---

**5.2.1.5 Neurological:**

Rule out non-inflammatory causes. If non-inflammatory cause, treat accordingly and continue protocol therapy.

Grade of neurological toxicity (NCI CTCAE v 4)	Management	Follow-up

Grade 1
 
 
• Asymptomatic or mild symptoms
 
• Intervention not indicated
 
	
 
• Continue nivolumab
 
	
 
• Continue to monitor the patient, if worsening treat as grade 2, 3, or 4
 

Grade 2
 
 
• Moderate symptoms
 
• Limiting instrumental ADLs
 
	
 
• Delay nivolumab
 
• Treat symptoms per institutional guidelines
 
• Consider 0.5-1mg/kg per day methylprednisolone IV or oral equivalent
 
	
 
• If returns to baseline, resume nivolumab and IL-2
 
• If worsens, treat as grade 3 or 4
 

Grade 3 or 4
 
 
• Severe symptoms
 
• Limiting self-care ADLs
 
	
 
• Discontinue nivolumab
 
• Consult Neurology
 
• Treat symptoms per institutional guidelines
 
• 1-2mg/kg per day IV methylprednisolone or IV equivalent
 
• Add prophylactic antibiotics for opportunistic infections
 
	
 
• If improves to grade 2, taper steroids over at least one month
 
• If worsens, consider IVIG or other immunosuppressive therapies per institutional guidelines
 

Meningitis or Encephalitis
	
 
• Discontinue nivolumab
 
• 1-2mg/kg per day IV methylprednisolone or IV equivalent
 
	
 
• If improves, convert to oral steroids (prednisone 60mg/day or equivalent)
 
• When symptoms
 

		improve to $\leq$ grade 1, taper steroids over at least one month
--	--	---

**5.2.1.6 Skin:**

Rule out non-inflammatory causes. If non-inflammatory cause, treat accordingly and continue protocol therapy

Grade of Rash (NCI CTCAE v4)	Management	Follow-up
Grade 1-2 Covering $\leq$ 30% body surface area (BSA)	
 
• Symptomatic therapy (such as antihistamines, topical steroids)
 
• Continue nivolumab
 
	
 
• If persists 1-2 weeks or recurs                             
 
○ Consider skin biopsy
 
○ Delay nivolumab and IL-2
 
○ Consider 0.5-1mg/kg/day methylprednisolone IV or oral equivalent
 
○ Once improving, taper steroids for at least one month
 
○ Consider prophylactic antibiotics for opportunistic infections like PCP
 
○ Resume nivolumab and IL-2 if rash improves to <math>\leq</math> grade 1 within 12 weeks and corticosteroids have been reduced to <math>\leq</math> 10 mg oral prednisone or equivalent per day
 
 
 
• If worsens, treat as grade 3 or 4
 

Grade 3-4 Covering $>$ 30% BSA or life threatening consequences	
 
• Delay or discontinue nivolumab.
 
• Consider skin biopsy
 
• Consult dermatology
 
• 1-2mg/kg/day methylprednisolone IV or IV equivalent
 
• Add prophylactic antibiotics for opportunistic infections
 
	
 
• If improves to grade 1:                             
 
○ Taper steroids over at least one month
 
○ Resume nivolumab and IL-2 if rash improves to <math>\leq</math> grade 1 within 12 weeks and corticosteroids have been reduced to <math>\leq</math> 10 mg oral prednisone or equivalent per day
 
 
 

**5.2.1.7 Renal:**

Rule out non-inflammatory causes. If non-inflammatory cause, treat accordingly and continue protocol therapy

Grade of elevation in serum creatinine (NCI CTCAE v4)	Management	Follow-up
Grade 1 Serum creatinine >ULN and >baseline but ≤1.5x baseline	
 
Continue nivolumab
 
Monitor serum creatinine weekly
 
	
 
If returns to baseline, resume creatinine monitoring per protocol
 
If worsens, treat as grade 2, 3, or 4
 

Grade 2 or 3 Serum creatinine 1.5x baseline to ≤ 6 x ULN	
 
Delay or discontinue nivolumab
 
Monitor serum creatinine every 2-3 days
 
0.5-1 mg/kg/day methylprednisolone IV or oral equivalent
 
Add prophylactic antibiotics for opportunistic infections
 
Consider renal biopsy
 
	
 
If improves to grade 1                             
 
Taper steroids over at least one month
 
Resume nivolumab and IL-2 if improves to ≤ grade 1 within 12 weeks and corticosteroids have been reduced to ≤ 10 mg oral prednisone or equivalent per day
 
 
 
If elevation persists >7 days or worsens, treat as grade 4
 

Grade 4 Serum creatinine <6x ULN	
 
Discontinue nivolumab
 
Monitor serum creatinine daily
 
1-2mg/kg/day methylprednisolone IV or IV equivalent
 
Add prophylactic antibiotics for opportunistic infections
 
Consult nephrology
 
Consider renal biopsy
 
	
 
If improves to grade 1                             
 
Taper steroids over at least one month
 
Resume nivolumab and IL-2 if improves to ≤ grade 1 within 12 weeks and corticosteroids have been reduced to ≤ 10 mg oral prednisone or equivalent per day
 
 
 

**For nivolumab only** with any grade 4 **hematologic toxicity**, hold nivolumab. If the adverse event improves to grade 3 or better with symptomatic management and/or supportive medications, nivolumab may be resumed in ≥2 weeks.

Discontinue both IL-2 and Nivolumab permanently for the following conditions:

- Guillain-Barre Syndrome (GBS)
- Myasthenia gravis
- Pituitary apoplexy or hypopituitarism (clinical including based on biochemical values).

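### Two dose-management tables print wrong thresholds: hepatic grade 2 overlaps grade 1 with opposite instructions, and the renal grade 4 sign appears reversed

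*Combined protocol and SAP*

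**What the plan says.** Section 5.2 makes CTCAE version 4.0 the grading standard, and the grade columns of the hepatic and renal tables name CTCAE v4. The renal table opens with "Rule out non-inflammatory causes. If non-inflammatory cause, treat accordingly and continue protocol therapy", and the hepatic table has the same condition.

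**Hepatic (5.2.1.4).** Grade 1 is AST/ALT above ULN to 3x ULN and/or bilirubin above ULN to 1.5x ULN; nivolumab continues. Grade 2 is printed as above ULN to 3-5x ULN for AST/ALT, and above ULN to 1.5-3x ULN for bilirubin. Nivolumab is delayed and prednisone 1-2 mg/kg/day is given. Grade 3-4 is AST/ALT above 5x and/or bilirubin above 3x ULN, and nivolumab is stopped.

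**Renal (5.2.1.7).** Grade 1 ends at 1.5x baseline. The next row is "Grade 2 or 3 Serum creatinine 1.5x baseline to ≤ 6 x ULN", with the action "Delay or discontinue nivolumab". If the elevation lasts more than 7 days or increases, the follow-up column routes it upward: "days or worsens, treat as grade 4". The last row is "Grade 4 Serum creatinine <6x ULN". It calls for stopping nivolumab, daily creatinine and 1-2 mg/kg/day IV methylprednisolone, and its follow-up column adds "Resume nivolumab and IL-2 if improves to ≤ grade 1 within 12 weeks".

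**Pointer (5.2, after nivolumab and before the second IL-2 cycle).** Toxicities of unclear attribution, liver test rises among them, are to be managed by tables placed in section 5.2.2. No such section exists; the tables are in 5.2.1.

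**The concern.** Each row of these tables should cover its own range, and severity should rise down the page. Two rows break that pattern.

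The hepatic overlap matters more, because the two rows it joins give opposite instructions. Section 3.1.5 admits patients with AST/ALT up to 2.5x ULN and bilirubin up to 1.5x ULN, so a patient can enter the trial inside the overlap. A site that followed the printed grade 2 row would withhold nivolumab and start steroids for a value that the row above says to continue through. It could also hold up IL-2: section 5.2 requires immune-mediated toxicity to be at grade 1 or better, and the patient to be off systemic steroids or at no more than 10 mg prednisone, before the second cycle. A dose of 1-2 mg/kg/day is well above that in any adult.

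The renal row fails the other way. Its printed criterion leaves out the most severe values, which are the ones it exists for.

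**Working it through.** The plan states no figure to reproduce. The check applies the printed bounds literally and then the corrected ones. All inputs are the bounds in 5.2.1.4 and 5.2.1.7, as multiples of ULN.

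**Hepatic, AST/ALT.** Printed: grade 1 is 1 < x ≤ 3; grade 2 is 1 < x ≤ 5; grade 3-4 is x > 5. Corrected grade 2: 3 < x ≤ 5.

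| AST/ALT | Printed rows met | Corrected row met |
|---|---|---|
| 1.2x, 2.5x, 3x | 1 and 2 | 1 |
| 4x, 5x | 2 | 2 |
| 6x | 3-4 | 3-4 |

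**Hepatic, bilirubin.** Printed: grade 1 is 1 < x ≤ 1.5; grade 2 is 1 < x ≤ 3; grade 3-4 is x > 3. Corrected grade 2: 1.5 < x ≤ 3.

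| Bilirubin | Printed rows met | Corrected row met |
|---|---|---|
| 1.2x, 1.5x | 1 and 2 | 1 |
| 2x, 3x | 2 | 2 |
| 3.5x | 3-4 | 3-4 |

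The figures 3-5x and 1.5-3x already printed in the grade 2 row fit exactly between grade 1 and grade 3-4. The error is the extra lower bound in front of them.

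**Renal, baseline creatinine 1.0x ULN.** Printed: grade 1 is 1 < x ≤ 1.5; grade 2-3 runs from 1.5 to 6 inclusive; grade 4 is x < 6. Corrected grade 4: x > 6.

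| Creatinine | Printed rows met | Corrected row met |
|---|---|---|
| 1.2x | 1 and 4 | 1 |
| 2x, 4x | 2-3 and 4 | 2-3 |
| 6x | 2-3 | 2-3 |
| 7x, 9x | none | 4 |

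A baseline of 0.8x gives the same pattern. At a baseline of 1.5x, grade 1 runs to 1.5 × 1.5 = 2.25x ULN, so 2x meets grades 1 and 4 as printed and grade 1 once corrected. The grade 2-3 row includes 6x ULN and sends worsening to grade 4, so grade 4 must start above 6x. That follows from the table alone.

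**Stop wording across the seven tables.** Seven instructions require nivolumab to be discontinued: pulmonary 3-4, gastrointestinal 4, hypophysitis 4, hepatic 3-4, neurological 3-4, meningitis or encephalitis, and renal 4. Only renal 4 also has a resume rule, so 1 of 7. Two further rows, skin 3-4 and renal 2-3, offer delay or discontinuation, and both have resume rules.

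**The case against.** **CTCAE selects the row.** Section 5.2 and the table headings tell the site to grade by CTCAE v4, so an investigator who grades first and then reads across will reach the right instruction. This stands, and it is the main reason expected harm is small. It does not make the printed numbers harmless, because the tables set numeric bounds beside each grade and a site may work from those.

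**The renal sign may be a file-reading error.** It is one character in a machine-read table. The gastrointestinal grade 3 row, split across a page, shows methylprednisolone with no dose, so some table text may have been lost. This stands as a reason to check the original. The other comparison signs in these tables read sensibly, and the hepatic error is less exposed because the extra lower bound appears for both AST/ALT and bilirubin.

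**Renal grade 4 can be followed as a temporary stop.** Where a stop is final the plan usually says so, as in "Permanently discontinue nivolumab and IL-2 for grade 4 hypophysitis" and the list headed "Discontinue both IL-2 and Nivolumab permanently for the following conditions", which does not include renal grade 4. A reader might infer that the row contradicts itself. The documents support only an ambiguity, since no other mandatory stop row has a resume rule.

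**Stronger readings that the documents do not support.** A reader might infer that the printed renal row would stop nivolumab in a patient with normal creatinine. The column grades elevations in creatinine, so a normal value does not enter the table. A reader might also infer that the misprints distort the count of dose-limiting toxicities, because section 11.1 defines these through 5.2.1. The count turns on grade 3 or 4 together. The hepatic grade 3-4 bounds are not misprinted. The renal table puts grades 2 and 3 in one row without printing the cut between them, so that grade has to come from CTCAE.

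**Conclusion.** The point holds as a minor correction. Two of seven organ tables misprint a threshold that governs dosing or steroids. The hepatic overlap covers AST/ALT from above 1x to 3x ULN and bilirubin from above 1x to 1.5x ULN, with opposite instructions in the two rows. The renal grade 4 criterion excludes every value above 6x ULN and overlaps the rows below it.

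The hepatic conclusion rests on the text alone. The renal one assumes that the printed sign is in the original document. Both intended bands can be recovered from adjacent rows, and the tables apply only once non-inflammatory causes are excluded. How many patients would fall in the overlap cannot be estimated from the documents.

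The Simon design (12 then 23 patients), its power and type I error, and the 2-of-3 and 6-of-10 safety rules are unaffected. The pointer to 5.2.2 is clerical: the only toxicity tables are in 5.2.1, so it cannot lead to a wrong one. The renal stop-and-resume wording is a question for the sponsor.

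**What to change.** 1. Hepatic grade 2: print AST/ALT >3x to 5x ULN and/or total bilirubin >1.5x to 3x ULN.
2. Renal grade 4: check the sign against the original document and, if it is as read here, change it to >6x ULN.

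Editorial notes for the same amendment:

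- In section 5.2, redirect the pointer from 5.2.2 to 5.2.1.
- Ask the sponsor whether the renal grade 4 stop is temporary. If so, call it a delay and keep the resume rule. If not, delete the resume rule and say whether that also covers a grade 2-3 rise sent there only for lasting more than 7 days. If the rule stays, state how its 12-week window fits with the rule in section 5.2 that ends study therapy after a toxicity delay of more than 6 weeks.

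The two thresholds and the pointer are wording changes. The renal stop needs one clinical decision. There is no statistical cost.

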### 5.3 Concomitant Medications/Treatments

Corticosteroids greater than the equivalent of 10mg daily of prednisone (except physiologic dose for adrenal replacement therapy), other immunosuppressive agents (such as cyclosporine or methotrexate) and any other medications that could potentially impact the efficacy or safety of the study as judged by the treating investigator are NOT permitted from time of registration to subjects completing protocol therapy unless clinically indicated to manage adverse events or life threatening or serious conditions as determined by the treating investigator.

**5.4 Other Modalities or Procedures**

Nivolumab should be held for any surgery or radiotherapy until subject is judged to be stable to resume by treating investigator as adequate information does not exist on its effects on wound healing and radio sensitization effects. When resumed, same dose level will be maintained. Percutaneous procedures like imaging guided biopsies and central line placements do not require Nivolumab to be held.

**5.5 Duration of Protocol Specified Therapy (IL2 and/or Nivolumab)**

In the absence of treatment delays due to adverse events, treatment may continue for up to 48 weeks or until one of the following criteria apply:

- Disease progression as defined in Section 7.0.
- Inter-current illness that prevents further administration of treatment
- Unacceptable adverse event(s)
- Patient voluntarily withdraws from treatment
- General or specific changes in the patient's condition render the patient unacceptable for further treatment in the judgment of the investigator

**5.6 Off Protocol Specified Therapy Criteria**

Patients will be removed from protocol specified therapy when any of the criteria listed in Section 5.5 apply. The reason for ending protocol therapy and the date the patient was removed from treatment should be documented. All patients who discontinue treatment should comply with protocol specific follow-up procedures as outlined in Section 6.3. The only exception to this requirement is when a subject withdraws consent for all study procedures or loses the ability to consent freely.

**5.7 Duration of Follow-Up**

Patients will be followed for 2 years (counting from week 1) after completion of/removal from treatment or until death, whichever occurs first. Patients removed from treatment for unacceptable adverse events will be followed until resolution or stabilization of the adverse events.

**5.8 Off Study Criteria**

Patients can be taken off study at any time at their own request, or they may be withdrawn at the discretion of the investigator for safety, behavioral or administrative reasons. The reason(s) for discontinuation from study will be documented and may include:

- 5.8.1 Patient withdraws consent (termination of treatment and follow-up);
- 5.8.2 Loss of ability to freely provide consent through imprisonment or involuntary incarceration for treatment;
- 5.8.3 Patient is unable to comply with protocol requirements in the judgment of the treating investigator;
- 5.8.4 Treating physician determines continuation on the study would not be in the patients best interest;
- 5.8.5 Patient becomes pregnant (pregnancy to be reported along same timelines as a serious adverse event);
- 5.8.6 Development of second malignancy (except for basal cell carcinoma or squamous cell carcinoma of the skin) that requires treatment, which would interfere with this study;
- 5.8.7 Lost to Follow-up. If a research subject cannot be located to document survival in the follow-up period per protocol, the subject may be considered "lost to follow-up." All attempts to contact such a subject during the follow-up period must be documented
- 5.8.8 Termination of the study by The University of Michigan or other regulatory bodies;
- 5.8.9 Patient completes protocol treatment and follow-up criteria.

**5.9 Patient Replacement**

Subjects who are not evaluable will be replaced. Evaluable patients are those who receive at least 1 dose of HD IL2 and at least 1 dose of nivolumab.

**6.0 STUDY PROCEDURES**

**6.1 Screening/Baseline Procedures (see Time and Events table section 6.4)**

Assessments performed exclusively to determine eligibility for this study will be done only after obtaining informed consent. Assessments performed for clinical indications (not exclusively to determine study eligibility) may be used for baseline values even if the studies were done before informed consent was obtained.

All screening procedures must be performed within 28 calendar days prior to registration unless otherwise stated. The screening procedures include:

**6.1.1 Informed Consent**

**6.1.2 Medical history**

To include complete medical and surgical history, history of infections, autoimmune diseases

**6.1.3 Demographics**

Age, gender

**6.1.4 Review subject eligibility criteria**

**6.1.5 Review previous (within 28 calendar days) and concomitant medications**

**6.1.6 Physical exam including vital signs, height and weight**

Vital signs (temperature, pulse, respirations, blood pressure), height, weight

**6.1.7 Performance status**

ECOG performance status

**6.1.8 Adverse event assessment**

Baseline adverse events will be assessed. See Section 8.0 for Adverse Event monitoring and reporting.

**6.1.9 Hematology**

CBC with diff includes total WBC, hemoglobin, hematocrit, platelet count and differential of the WBC including absolute counts

**6.1.10 Blood draw for correlative studies and anti-drug antibody analysis**

See Section 10.0 for details.

**6.1.11 Serum chemistries**

Comprehensive metabolic profile (COMP) includes sodium, potassium, chloride, bicarbonate, BUN, creatinine, AST, ALT, alkaline phosphatase, total bilirubin.

Magnesium, phosphorus, LDH.

TSH, free T3, free T4 (Only If Clinically Indicated: FSH, LH, ACTH).

**6.1.12 Coagulation**

PT/INR

**6.1.13 Urine Tests**

Urine protein/creatinine ratio

**6.1.14 Pregnancy test (for females of child bearing potential)**

Women of non-childbearing potential are defined as those who have no uterus, ligation of the fallopian tubes, or permanent cessation of ovarian function due to ovarian failure or surgical removal of the ovaries. All others are considered women of child bearing potential.

Either urine or serum pregnancy test is acceptable.

**6.1.15 Tumor assessment**

To be performed within 28 calendar days of registration: Computed tomography of the chest, computed tomography or magnetic resonance imaging of the abdomen and pelvis, computed tomography or magnetic resonance imaging of the brain

**6.1.16 Other**

- 12-lead Electrocardiography.

- High dose Interleukin-2 eligibility assessment: to be done within 4 weeks of registration, should include cardiac (including dobutamine stress echocardiogram or equivalent at the discretion of the treating investigator) and pulmonary function testing evaluation.
- An archived tissue block must be identified (but not needed to be submitted) to submit unstained slides from prior to registration.

## 6.2 Procedures During Treatment

**All assessments have a window of  $\pm$  3 business days except for imaging/tumor measurements where a window of  $\pm$  7 business days will apply.**

### 6.2.1 Each HD IL2 week (weeks 1 and 3)

- Physical exam, vital signs, ECOG Performance Status, Toxicity.
- Minimum of once daily: urine output measurement, pulse oximetry measurement.
- Hematology: CBC with diff includes total WBC, hemoglobin, hematocrit, platelet count and differential of the WBC including absolute counts
- Serum chemistries: Comprehensive metabolic profile (COMP) includes sodium, potassium, chloride, bicarbonate, BUN, creatinine, AST, ALT, alkaline phosphatase, total bilirubin.
- Magnesium, phosphorus, LDH
- Day 5 and Day 19 (N.B: these will occur during IL2 weeks): Total Creatinine Kinase, Troponin T
- Central line placement prior to any IL2 dose on days 1 and 15.
- HD IL-2 administration will start on Day 1 and continue every 8 hours until Day 5 (cycle 1), then resume on D15 and continue until D19 (cycle 2). HD IL2 dose strength (600,000 IU/kg/dose) will be calculated separately on Day 1 and Day 15 and not modified at other times during the IL2 week. IL2 dose will be administered over 15 minutes ( $\pm$  5 minutes) via a central line.
- Other clinical, laboratory and imaging assessments during HD IL-2 administration as per institutional guidelines per treating investigator

